10.6.3.3. Time to Rescue

Time to Stopping Randomized Treatment Due to Meeting Rescue Criteria
Meeting Rescue Evaluation Criteria and Rescue Criteria

 Subjects meeting evaluation criteria for rescue are identified from the Rescue Treatment eCRF. Subjects with a record on this form are considered to have met evaluation criteria for rescue. It is possible that a subject could be evaluated for rescue more than once, and in that case a subject would have multiple records on this form. Subjects unable to be evaluated for rescue are subjects who met evaluation criteria for rescue, but were unable to be assessed at the 4 week check (e.g., subjects who died, permanently discontinued randomized treatment or withdrew from the study before the 4 week check). The outcome of initial intervention eCRF field on the Rescue Treatment eCRF will be blank for these subjects. Subjects meeting rescue are identified by the response 'Met rescue criteria' to the outcome of initial intervention question on the Rescue Treatment eCRF.
Event Date

 Treatment stop date when the primary reason and subreason for randomized treatment stop are: 
 Primary reason: Subject reached protocol-defined stopping criteria Subreason: Rescue
General Definitions

 Time to event (days) = date of event – randomization date +1 Censored time (days) = censoring date – randomization date + 1 Rescue person years = (cumulative total time to stopping randomized treatment for subjects

Time to Stopping Randomized Treatment Due to Meeting Rescue Criteria

who stopped randomized treatment due to meeting rescue criteria + cumulative total of censoring time for subjects who did not stop randomized treatment due to meeting rescue criteria) / 365.25
 
 • Rescue incidence rate (per 100 person years) = (100 * number of subjects who stopped randomized treatment due to meeting rescue criteria) / rescue person years • Rescue absolute rate difference (per 100 person years) = daprodustat rescue incidence rate (per 100 person years) – darbepoetin alfa rescue incidence rate (per 100 person years)
Time Period for Treatment Discontinuation

The period for treatment discontinuation begins at randomization. The end of this time period is defined as follows:
 
 • For subjects who did not take randomized treatment, use the date of randomization • For subjects whose treatment stop date is missing and who took randomized treatment, use study conclusion date • For subjects either continuing on study past treatment stop date or completing/withdrawing on the same day as treatment stop date, use treatment stop date 
Any events that occurred before the start of this time period are considered to be prior to the time period for treatment discontinuation, and any endpoints that occurred after the end of this time period are considered to be post the time period for treatment discontinuation.

10.6.3.4. RBC and Whole Blood Transfusion Endpoints

Number of RBC and Whole Blood Transfusions	

 • The number of transfusions associated with each RBC and Whole Blood Transfusion record is determined by the frequency, start date, end date and number of units, as described below. • Only on-treatment transfusions are included. “End date” below refers to the end date defined for the transfusion, or the end of the on-treatment period, if sooner (see Section 10.4.1). • For records with a frequency of “Once only” or “Continuous infusion”, each record is considered to be a single transfusion (regardless of start and end dates or number of units) • For records with a frequency of “Once daily”, the number of transfusions will equal the duration (end date – start date +1). • For records with a frequency of “PRN”, or where the frequency is unknown, the number of transfusions for each record will be equal to the number of units recorded. • For other transfusion records, the number of transfusions will equal the duration (end date – start date +1) times a multiplier, as defined below: The number of transfusions should be rounded up to the nearest integer. 	
Frequency	Multiplier
QM	0.033
Every 2 weeks	0.071
Once a week	0.14
Q4D	0.25

2 times per week	0.29
Q3D	0.33
3 times per week	0.43
Every other day	0.5
4 times per week	0.57
5 times per week	0.71
BID	2
Q12H	2
TID	3
Q8H	3
QID	4
Q6H	4
5 times per day	5
Q4H	6

Number of RBC and Whole Blood Transfusion Events

- RBC and Whole Blood Transfusion Events are defined by grouping together on-treatment transfusion records.
- Transfusion records are grouped into the same Transfusion Event if the transfusion start/end dates match with or are contained within an Admission/Discharge period, (based on the Hospitalization page in the eCRF).
- For example, the following transfusion records would be grouped into a single Transfusion Event, because each transfusion is contained within the same hospital admission/discharge period:

Dose	Frequency	Transfusion Dates		Hospitalisation		Comment
		Start Date	End Date	Admission	Discharge	
1 unit	Once only	16FEB2019	16FEB2019	15FEB2019	26FEB2019	1 Transfusion Event
1 unit	Once only	19FEB2019	19FEB2019	15FEB2019	26FEB2019	

- Transfusion records not matching with an Admission/Discharge period are considered to be the same Transfusion Event if the gap between transfusions is 5 days or less, with further details provided below. For any subject where the frequency is PRN and the transfusion start date ≠ end date, the dates of individual transfusions are unknown and the number of transfusion events will be counted as one.
- In the case of a sequence of more than two transfusions, transfusions are considered to be the same Transfusion Event if the gap between each transfusion and the start date of the first transfusion in the sequence (the “anchor” transfusion) is 5 days or less. The first transfusion that is greater than 5 days after the “anchor” transfusion is not included in the Transfusion Event, and it becomes the new “anchor” transfusion for a new Transfusion Event.
- In the example below, transfusion records 1 and 2 would be grouped into a single Transfusion

Event, because the gap between the transfusions (17JAN2019 to 18JAN2019) was 5 days or less. Record 3 falls outside this Transfusion Event because the gap between the start date (22JAN2019) and the previous anchor date (16JAN2019) is more than 5 days. Therefore, 22JAN2019 becomes the new “anchor” transfusion used to define the next Transfusion Event. This pattern is repeated, if necessary. N.B. “anchor” transfusions are shown in bold.

#	Dose	Frequency	Transfusion Dates		Comment
			Start Date	End Date	
1	1 unit	Once only	16JAN2019	16JAN2019	1 Transfusion Event
2	1 unit	Once only	19JAN2019	19JAN2019	
3	1 unit	Once only	22JAN2019	22JAN2019	1 Transfusion Event
4	1 unit	Once only	25JAN2019	25JAN2019	
5	1 unit	Once only	28JAN2019	28JAN2019	1 Transfusion Event

Where a non-integer number of units has been entered on the eCRF, this will be rounded up to the nearest integer prior to any subsequent derivation (if necessary).

Number of Units

- The number of RBC and whole blood units are derived from blood transfusion records. The number of units associated with each record is determined by the frequency, start date, end date and dose (i.e. number of units recorded), as described below:
- Only units associated with on-treatment transfusions are included. “End date” below refers to the end date defined for the transfusion, or the end of the on-treatment period, if sooner (see Section 10.4.1).


 • Only transfusion events with a start date from date of week 28 visit to the date of the week 52 visit will be included • Patient Years (PY) = (cumulative total time from date of week 28 visit to the date of the week 52 visit, for subjects who did not withdraw from randomized treatment during the evaluation period + cumulative time from date of week 28 visit to the date of withdrawal from randomized treatment, for subjects who withdrew from randomized treatment during the evaluation period) / 365.25 • Transfusion Events per 100 PY = (100 * number of on-treatment RBC or whole blood transfusion events during the evaluation period) / Patient Years (PY) • Transfusions per 100 PY = (100 * number of on-treatment RBC or whole blood transfusions during the evaluation period) / Patient Years (PY) • Units per 100 PY = (100 * number of on-treatment RBC or whole blood transfusion units during the evaluation period) / Patient Years (PY)
Randomization to Week 52

 • Only transfusion events with a start date from the date of randomization to the date of the week 52 visit will be included • Patient Years (PY) = (cumulative total time from date of randomization to the date of the week 52 visit, for subjects who did not withdraw from randomized treatment prior to week 52 + cumulative time from date of randomization to the date of withdrawal from randomized treatment, for subjects who withdrew from randomized treatment prior to week 52) / 365.25 • Transfusion Events per 100 PY = (100 * number of on-treatment RBC or whole blood transfusion events from the date of randomization to the date of the week 52 visit) / Patient Years (PY) • Transfusions per 100 PY = (100 * number of on-treatment RBC or whole blood transfusions from the date of randomization to the date of the week 52 visit) / Patient Years (PY) • Units per 100 PY = (100 * number of on-treatment RBC or whole blood transfusion units from the date of randomization to the date of the week 52 visit) / Patient Years (PY)
Randomization to End of Treatment

 • Person Years (PY) = (cumulative total time from date of randomization to the study conclusion date, for subjects who did not withdraw from randomized treatment + cumulative time from date of randomization to the date of withdrawal from randomized treatment, for subjects who withdrew from randomized treatment) / 365.25 • Transfusion Events per 100 PY = (100 * number of on-treatment RBC or whole blood transfusion events from the date of randomization to the date of study conclusion or withdrawal from treatment) / Person Years (PY) • Transfusions per 100 PY = (100 * number of on-treatment RBC or whole blood transfusions from the date of randomization to the date of study conclusion or withdrawal from treatment) / Person Years (PY) 
Units per 100 PY = (100 * number of on-treatment RBC or whole blood transfusion units from

the date of randomization to the date of study conclusion or withdrawal from treatment) / Person Years (PY)
Time to First On-Treatment RBC or Whole Blood Transfusion

 Event Date = Start date for the first on-treatment RBC or whole blood transfusion received after treatment start Censoring Date = date of stopping randomized treatment for subjects who stopped randomized treatment, or date of study completion for subjects who did not stop randomized treatment Time to event (days) = date of event – treatment start date +1 Censored time (days) = censoring date – treatment start date + 1

 Person years (PY) = (cumulative total time to event date, for subjects who received at least one on-treatment RBC or whole blood transfusion + cumulative total of censoring time for subjects who did not receive at least one on-treatment RBC or whole blood transfusion) / 365.25 Incidence rate per 100 PY = (100 * number of subjects who received at least one on-treatment RBC or whole blood transfusion) / person years 
Absolute rate difference (per 100 person years) = daprodustat incidence rate (per 100 person years) – darbepoetin alfa incidence rate (per 100 person years)

Time Period for On-Treatment Transfusions

 The period for capturing on-treatment transfusions begins on the treatment start date +1 day. The end of this time period is defined as follows: 
 For subjects continuing on study past the (treatment stop date + 1 day), use (treatment stop date + 1 day) For subjects whose study withdrawal/completion date is on or before (treatment stop date + 1 day), use date of study withdrawal/completion
Model Specification

 Analysis of time to first RBC or whole blood transfusion will be performed using an analysis model identical to that described for the co-primary MACE analysis (Section 7.2.2) for the evaluation of superiority. Analysis will include only transfusion occurring during the on-treatment period.
Model Results Presentation

 The model results presentation will be identical to the co-primary MACE model results, with the following exception: A single one-sided p-value for the test of superiority of daprodustat vs. darbepoetin alfa will be presented (i.e. there will be no test for non-inferiority). A Kaplan-Meier plot will be produced showing the survival function for time to first RBC or whole blood transfusion.

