The number and percentage of subjects that met the iron management criteria during the study while on treatment will be summarized by treatment group for each 3-month period of the study, the first year and across the entire study. There are two types of iron management thresholds: the first type requires that iron therapy be administered if subjects have ferritin and/or TSAT values that are too low; the second type requires that all iron (excluding multivitamins) must be stopped if ferritin and/or TSAT values are too high. It is also possible for a subject to meet starting and stopping criteria on the same day with a low ferritin and a high TSAT. These subjects will also be summarized (see Section 10.6.3). Assessment of meeting iron management thresholds will be made based on central laboratory data values at the scheduled visits for ferritin and TSAT assessments, according to the schedule outlined in the Time and Events table (see Section 10.2.1).

RBC and Whole Blood Transfusions

Summary and analysis tables will use the ITT population.

The total number of on-treatment RBC and whole blood transfusion events, transfusions and units for each subject will be derived as described in Section [10.6.3.4](#).

The number of on-treatment RBC and whole blood transfusion events per subject, the number of subjects with at least one RBC and whole blood transfusion event, and total number of RBC and whole blood transfusion events will be summarized.

The number of on-treatment RBC and whole blood transfusions events per 100 patient years will be summarized by treatment group.

The number of on-treatment RBC and whole blood transfusions per 100 patient years will be summarized by treatment group.

The number of on-treatment RBC and whole blood units per 100 patient years will be summarized by treatment group.

The reason for transfusion events will be summarised.

The above summaries will be produced for the Evaluation Period, Week 52 and End of Treatment.

An analysis of time to first RBC or whole blood transfusion will be performed as described in Section [10.6.3.4](#)., including a Kaplan-Meier plot.

DGF

Delayed graft function after deceased donor kidney transplantation is defined in Section [10.6.3](#).

The number and percentage of patients experiencing DGF after deceased donor kidney transplantation will be summarized by treatment group.

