
 • Date of withdrawal for subjects withdrawing (i.e., subjects who actively withdraw or are deemed lost to follow-up) from study or date of completion of study for subjects who complete the study. If the date of study withdrawal entered in the eCRF is before the last study contact date, the last study contact date will be used as the study withdrawal date for analysis. 
 • Note: Subjects who die while on study are considered as having completed the study • The eCRF allows for the possibility of missing or partial dates to be recorded for the study completion/withdrawal date on the Study Conclusion form (i.e., missing day, or day and month, or day and month and year). In such a case, or in case of subjects who are missing a Study Conclusion form, the following conventions will be applied in order to impute a study completion/withdrawal date: 
 • Missing day: 
 ▪ The last day of the month will be used, unless the last study contact date also occurs in the same month; in the case, the last study contact date will be used. • Missing day and month: 
 ▪ '31' will be used for the day and 'Dec' will be used for the month, unless the last study contact date also occurs in the same year; in this case, the last study contact date will be used. • Missing day, month and year: 
 ▪ The last study contact date will be used. • If both death and study completion/withdrawal have missing or partial dates, they will be imputed as specified (see Section 10.6.1 and Section 10.6.4). If the imputed death date is prior to the imputed study completion/withdrawal date, then the study completion/withdrawal date will use the imputed death date instead.
Planned/Actual Visit Dates

 • Planned/actual visit dates will be defined as follows: 
 ○ Week 28 date: Non-missing Week 28 visit start date (from SV domain), otherwise randomization date + 28*7 ○ Week 36 date: Non-missing Week 36 visit end date (from SV domain), otherwise randomization date + 36*7 ○ Week 52 date: Non-missing Week 52 visit end date (from SV domain), otherwise randomization date + 52*7 ○ End of Study date: Non-missing End of Study visit start date (from SV domain), otherwise the middle of the End of Study window.
Stabilization Period

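### The evaluation-period transfusion rates give Week 28 to 52 person-time to subjects already off randomized treatment, while counting only on-treatment transfusions, so these descriptive rates come out too low

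*SAP*

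**What the plan says.** SAP section 10.6.3.4 builds the EP patient-years from two groups only.

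- The first is given the whole span between the Week 28 and Week 52 visits. Its membership is set by the words "for subjects who did not withdraw from randomized treatment during the evaluation period".
- The second contributes time from the Week 28 visit to treatment withdrawal, and is defined as the time "for subjects who withdrew from randomized treatment during the evaluation period".

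The numerator of the event rate is the "number of on-treatment RBC or whole blood transfusion events during the evaluation period"; the transfusion and unit rates are built the same way. For on-treatment transfusions the same section closes the window as follows: "For subjects continuing on study past the (treatment stop date + 1 day), use (treatment stop date + 1 day").

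Section 8.1.2.2 sets the population and the reporting windows: "Summary and analysis tables will use the ITT population", and "The above summaries will be produced for the Evaluation Period, Week 52 and End of Treatment".

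For a subject without a Week 28 visit, section 10.6.1 supplies a planned date: "otherwise randomization date + 28*7". The Week 52 date follows the same pattern.

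**The concern.** The two groups do not separate subjects on treatment at Week 28 from those already off it. Someone who stopped at Week 20 did not withdraw during the EP, so the wording places that person in the first group with the full 24 weeks. The on-treatment window for that person closed long before, so no event can be counted. Person-time and events then describe different sets of people.

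This case will occur. Section 10.7.1 says that subjects who stop study drug are encouraged to remain in the study, and the schedule for them in section 10.2.1.3 includes visits at Weeks 28 and 52. They therefore have actual visit dates, and the main point does not depend on planned dates.

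At stake are three reported rates per arm in one of three pre-specified windows. As worded, they are also not comparable with the rates for the other two windows, which use on-treatment person-time.

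**Working it through.** The SAP states no numerical rate, so there is no figure to reproduce. The check applies the stated person-time rule as written and compares it with on-treatment person-time.

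**One subject who stops treatment at Week 20 and stays in the study**

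- EP denominator as written: 24 × 7 / 365.25 = 0.460 patient-years. On-treatment time in the EP: 0.
- Randomization to Week 52 denominator: 20 × 7 / 365.25 = 0.383 patient-years, which is the true on-treatment time. That formula asks whether treatment was withdrawn at any time before Week 52, so it catches early stoppers.

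**All subjects**

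Let d be the share of subjects given EP time who stopped before Week 28, e the share of the rest who stop during the EP (on average halfway through), and T = 0.460 years. Neither d nor e is in the SAP; both are assumptions.

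- On-treatment patient-years per subject: (1 − d)(1 − e/2)T
- Patient-years as written: (1 − d)(1 − e/2)T + dT
- Reported rate / on-treatment rate: (1 − d)(1 − e/2) / [(1 − d)(1 − e/2) + d]

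With e = 0 this is exactly 1 − d.

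Example with 1,000 subjects, d = 10%, e = 10% and an assumed on-treatment rate of 15 per 100 patient-years: on-treatment time is 393.3 and time as written is 439.3 patient-years. Events are 0.15 × 393.3 = 59.0. The reported rate is 100 × 59.0 / 439.3 = 13.4.

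| d | Factor, e = 0 | Factor, e = 10% | Reported rate if the true rate is 15, e = 10% |
|---|---|---|---|
| 5% | 0.950 | 0.948 | 14.2 |
| 10% | 0.900 | 0.895 | 13.4 |
| 15% | 0.850 | 0.843 | 12.7 |
| 20% | 0.800 | 0.792 | 11.9 |
| 30% | 0.700 | 0.689 | 10.3 |

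Setting the person-time of pre-Week 28 stoppers to zero recovers 15.0 in every row.

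**Comparison with other definitions in the SAP**

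- Randomization to Week 52 and Randomization to End of Treatment (section 10.6.3.4): both end person-time at treatment withdrawal for anyone who withdrew earlier.
- Time to first transfusion (section 10.6.3.4): censored when randomized treatment stops.
- Percent time in range during the EP (section 10.6.3.1): requires a treatment stop date on or after Week 28.

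Only the EP transfusion denominator has no such limit.

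**The case against.** The strongest reply is that the wording is loose rather than wrong. The numerator is on-treatment, and the neighbouring formula stops person-time at treatment withdrawal, so a sensible programmer might take the first group to mean subjects on treatment when the EP begins. That is probably the intent. But no sentence says so, the ITT population does not remove early stoppers, and the text followed as written gives a different denominator.

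Three stronger readings are tempting, and the SAP does not support them.

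- **That the between-arm comparison is biased.** Unequal early stopping would distort a ratio of the two rates: with 10% v 20% stopped, e = 10% and equal true rates, it would be 11.9 / 13.4, about 0.88. But no EP rate ratio or test is planned. Table 6 lists these rates as summaries, and section 2.2 places them among exploratory endpoints without planned testing. The only modelled transfusion analysis is time to first transfusion, which has its own person-time.
- **That subjects who died or left the study before Week 28 certainly receive EP time.** They do only if the planned-date convention of section 10.6.1 is carried into this formula, which refers simply to the visit dates. The general EP definition uses planned or actual dates, so this is plausible but remains an inference.
- **That the rates are off by a known percentage.** The share who stopped before Week 28 is not given.

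It also stands that correctly defined rates for the other two windows will appear beside the EP rates.

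**Conclusion.** The point holds for the EP denominator as worded. The direction is certain whenever at least one subject who stopped before Week 28 receives EP time and at least one on-treatment EP transfusion is counted: all three rates are too low. The size is about the share of such subjects, so roughly 10% too low if 10% stopped and 20% too low if 20% stopped. It is slightly more if others stop during the EP. These shares are assumptions.

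The consequence is limited to exploratory, descriptive summaries. No co-primary, principal secondary or other tested result changes.

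**What to change.** In the EP part of section 10.6.3.4, limit patient-years to subjects still on randomized treatment at the Week 28 date. Count from that date to the earliest of the Week 52 date, the date of withdrawal from randomized treatment, and study withdrawal or completion. Ending at the treatment withdrawal date keeps the EP denominator in line with the Week 52 and End of Treatment denominators. The numerator's one-day allowance after the treatment stop date need not be added to the person-time.

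The cost is one clause of SAP wording. No new data or analysis is needed, and the reported EP rates will be somewhat higher than under the present text.

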
 • To further compare daprodustat and darbepoetin alfa on Hgb variability 	
 • Hgb observed and change from baseline across all visits to end of treatment • % of time Hgb is above, within and below the range of 10-11.5 g/dL during EP and MP • Number (%) of subjects with mean Hgb above, within and below the Hgb analysis range during EP and at the end of treatment • Number (%) of subjects with a Hgb <7.5 g/dL during the EP and MP • Number of times Hgb <7.5 g/dL during the EP and MP • Number (%) of subjects with a >1g/dL increase in Hgb over 2 weeks (assessed at Week 2 and Week 4) or a >2 g/dL increase in Hgb within any 4 week period from Week 4 to Week 52 • Number (%) of subjects with a >1g/dL decrease in Hgb over 2 weeks (assessed at Week 2 and Week 4) or a >2 g/dL decrease in Hgb within any 4 week period from Week 4 to Week 52 • N (%) of subjects with a Hgb value \geq 12 g/dL during the EP and MP • Number of times Hgb \geq 12 g/dL during the EP and MP • % of time Hgb \geq 12 g/dL during the EP and MP

 • To compare daprodustat to darbepoetin alfa on measures of iron parameters 	
 • Observed and change from baseline in hepcidin, ferritin, TSAT, total iron, TIBC across all visits to end of treatment • Average quarterly ferritin • Average quarterly TSAT • N (%) of subject who met iron management criteria

 • To further compare daprodustat to darbepoetin alfa on BP and BP medication changes 	
 • Observed and change from baseline in SBP, DBP and MAP by visit • Number of BP medications per subject by visit • Change from baseline in the number of BP medications per subject by visit • N (%) of subjects who had no change, an increase or a decrease in the dosage or number of BP medications from baseline by visit

 • To compare daprodustat to darbepoetin alfa on the need for RBC and whole blood transfusions 	
 • Number (%) of subjects who receive at least one RBC or whole blood transfusions by Week 52 and by end of treatment • Number of RBC and whole blood transfusions per 100 patient years

Objectives	Endpoints
	
 Number of RBC and whole blood units per 100 patient years

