10.2.1.3. Schedule of Assessments for Subjects Permanently Discontinuing Randomized Treatment

Protocol Activity (Note: All visit timings are relative to Day 1)	Early Treatment Discontinuation Visit (within 2 weeks of discontinuing randomized treatment)	Day 1 through Week 52	
		Week 4, 16, 28, 40, 52 ± 2 weeks ⁷	Unscheduled
IRT system transaction	X		
SBP/DBP, HR	X (triplicate)	X	X
EKG	X		
Iron therapy, transfusions ¹	X	X	X
Urine (serum if transitioned to dialysis) pregnancy test (FRP only)	X ⁸		
HemoCue Hgb	X	X	X
Hematology ³	X	X	
Clinical chemistry ³	X	X	
Ferritin, total iron, UIBC, hepcidin, lipids, iPTH	X		
Hospitalization ¹ , transition to dialysis ¹ , kidney transplant ¹	X	X	X
Non-serious AEs, AEs of special interest, SAEs, clinical events	X	X	X
Review concomitant medications	X	X	X
Healthcare resource utilization (subject-reported)	X		
CKD-AQ. ^{5, 10}	X		
PGI-S, PGI-C ^{5, 10}	X		
SF-36 ^{5, 10}	X		
EQ-5D-5L & EQ-VAS ^{5, 6, 10}	X		
WPAI-ANS-CPV ^{4, 5, 10}	X		
ADPKD subjects only: Ultrasound	X ¹²		
ABPM sub-study (Appendix 13): 24 hour ABPM		X (Week 16)	
Record awake and sleep times		X (Week 16) ²	
24 hour urine collection (sodium, aldosterone & creatinine)		X (Week 16) ¹¹	

Schedule of Assessments for Subjects Permanently Discontinuing Randomized Treatment (Continued)

Protocol activity (visits ± 2 week) (Note: All visit timings are relative to Day 1)	Year 2 ⁷				Year 3 ⁷				Year 4 ⁷					Unscheduled	End of Study ⁹
	Week 64	Week 76	Week 88	Week 100	Week 112	Week 124	Week 136	Week 148	Week 160	Week 172	Week 184	Week 196	Week 208		
IRT system call															X
SBP/DBP, HR	X	X	X	X	X	X	X	X	X	X	X	X	X	X	X
HemoCue Hgb	X	X	X	X	X	X	X	X	X	X	X	X	X	X	
Hematology ³	X	Hgb only	X	Hgb only	X	Hgb only	X	Hgb only	X	Hgb only	X	Hgb only	X		X
Clinical chemistry ³	X		X		X		X		X		X		X		X
Hospitalization ¹ , transition to dialysis ¹ , kidney transplant ¹	X	X	X	X	X	X	X	X	X	X	X	X	X	X	X
Non-serious AEs, SAEs, AEs of special interest, clinical events	X	X	X	X	X	X	X	X	X	X	X	X	X	X	X
Review concomitant medications	X	X	X	X	X	X	X	X	X	X	X	X	X	X	X
Transition to dialysis ¹	X	X	X	X	X	X	X	X	X	X	X	X	X	X	X
ADPKD subjects only: eGFR ¹³		X		X		X		X		X		X			

1. Record in eCRF, if applicable.
2. Subject will record sleep and wake time during the ABPM session.
3. See details on hematology and clinical chemistry in Protocol Section 7.4.11.
4. If local dialect or language is available.

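### All transfusion endpoints, including the ITT percentage transfused by Week 52, stop counting when treatment stops; a Week 52 version counting all post-randomization transfusions should be added

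*SAP*

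**What the plan says.** SAP Section 2.2 lists, under the exploratory objective on the need for transfusion, "Number (%) of subjects who receive at least one RBC or whole blood transfusions by Week 52 and by end of treatment". Section 8.1.2.2 assigns these tables to the ITT population and asks for them over the evaluation period, to Week 52 and to end of treatment.

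Section 10.6.3.4 then restricts the counting: "Only on-treatment transfusions are included". Section 10.4.1.1 closes the on-treatment state for transfusion data one day after the treatment stop date. Patient-years in all three periods end at withdrawal from randomized treatment.

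For time to first transfusion, a subject without an event is censored at the "date of stopping randomized treatment for subjects who stopped randomized treatment", or at study completion otherwise. On events the model specification says: "Analysis will include only transfusion occurring during the on-treatment period". The analysis is done "using an analysis model identical to that described for the co-primary MACE analysis", with a Kaplan-Meier plot, and "A single one-sided p-value for the test of superiority of daprodustat vs. darbepoetin alfa will be presented".

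The schedule for subjects who have permanently discontinued treatment (Section 10.2.1.3) keeps a row for "Iron therapy, transfusions" at the discontinuation visit, at the visits through Week 52 and at unscheduled visits. The continuation of that table for Years 2 to 4 has no such row.

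**The concern.** Two consequences follow from the rules as written.

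First, the percentage transfused by Week 52 has all randomized subjects in its denominator, but its numerator can only grow while a subject is on treatment. An arm whose subjects stop earlier has less time in which a transfusion can count, so its percentage is lower for that reason alone.

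Second, stopping for rescue is a permanent stop of randomized treatment (Sections 2.2 and 10.6.3.3), so a subject not yet transfused is censored at that moment. Cox and Kaplan-Meier methods assume that censored subjects have the same later risk as those still followed. If risk is raised after a rescue stop and such stops are more frequent in one arm, that arm looks better than complete follow-up would show. A one-sided superiority p-value is to be attached to this comparison.

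No version using off-treatment transfusions is planned. The two co-primary endpoints each have both: treatment policy (hemoglobin) or all-randomized follow-up (MACE) as the main analysis, and a while-on-treatment analysis in support (Sections 7.1.2.4, 7.1.2.5 and 7.2.2).

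**Working it through.** The SAP gives no transfusion or rescue rate, so there is no stated figure to reproduce. The rules can be followed through directly; the sizes below rest on assumed inputs.

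**Following the rules.** A subject stops treatment at Week 20, stays in the study and is first transfused at Week 22. The transfusion falls later than stop date + 1 day, so it is off-treatment. The subject is counted as not transfused by Week 52 and is censored at Week 20 in the time-to-event analysis. The Week 22 transfusion is scheduled to be recorded.

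**Effect on the Week 52 percentage.** Assume a constant transfusion hazard λ per year that does not change after stopping, and a total treatment-stop hazard s. Ignoring the one-day allowance, deaths and withdrawals:

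- percentage under the SAP rule = λ/(λ+s) × (1 − exp(−(λ+s)))
- percentage counting all transfusions = 1 − exp(−λ)

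Take λ = 0.10, other stops 0.15, and rescue stops 0.03 or 0.06, so that s = 0.18 or 0.21:

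- s = 0.18: 0.10/0.28 × (1 − 0.7558) = 8.7%
- s = 0.21: 0.10/0.31 × (1 − 0.7334) = 8.6%
- all transfusions, either arm: 1 − 0.9048 = 9.5%

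Both percentages are understated, and slightly more so in the arm with more stops, even though the transfusion risk is identical and does not rise after stopping.

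**Effect on the rate ratio.** A simulation with 1,000,000 subjects per arm over 2 years used the same on-treatment hazard in both arms, so the true on-treatment ratio is 1. Other stops were 0.15 per year. The transfusion hazard in the three months after a rescue stop was multiplied by 1, 5 or 10. Ratios are first arm over second arm, in first events per person-year.

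| On-treatment hazard | Rescue-stop hazards | Multiplier after rescue | SAP rule | Follow-up after stop |
|---|---|---|---|---|
| 0.05 | 0.03 vs 0.06 | 5 | 0.998 | 0.979 |
| 0.05 | 0.03 vs 0.06 | 10 | 1.001 | 0.956 |
| 0.05 | 0.06 vs 0.03 | 5 | 0.991 | 1.013 |
| 0.05 | 0.06 vs 0.03 | 10 | 0.994 | 1.038 |
| 0.10 | 0.03 vs 0.06 | 5 | 0.997 | 0.976 |
| 0.10 | 0.03 vs 0.06 | 10 | 0.992 | 0.953 |
| 0.10 | 0.06 vs 0.03 | 5 | 1.001 | 1.020 |
| 0.10 | 0.06 vs 0.03 | 10 | 0.996 | 1.042 |

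The departures from 1.00 in the SAP-rule column are simulation noise. Continued follow-up shows a difference of about 1 to 5% that the SAP rule does not. With a multiplier of 1 the two columns agree. With equal rescue (0.03 in both arms) both ratios stay near 1, but with a multiplier of 5 or 10 each arm's rate is understated by about 2 to 5%, for example 5.02 against 5.26 per 100 person-years.

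**The case against.** The strongest reply is that this is a declared estimand on an exploratory endpoint. The time-to-event derivation has on-treatment in its title, the restriction is repeated throughout, and numerator and person-time are cut at the same point apart from one day. Week 52 and end of treatment can be read as two time horizons, so the SAP does not contradict itself. An imbalance in rescue would not be hidden, because time to stopping for rescue is a secondary endpoint with its own model (Section 8.1.1.2). The p-value lies outside the multiplicity-controlled family. All of this stands, and it is why the on-treatment analysis should not be replaced.

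Two stronger readings are tempting and are not supported.

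- A reader might infer that rescue stops censor subjects exactly when transfusion is most likely. The rescue criteria are in the protocol, not in this SAP. Section 10.6.3.3 describes an initial intervention followed by a 4-week check, and a transfusion in that interval on randomized treatment does count. The peak in risk could therefore precede the stop. A raised risk afterwards is plausible but remains an inference.
- A reader might put the bias near 10 to 20%. Assuming 8 transfusions per 100 person-years, 40% transfused after a rescue stop, and rescue stops of 4 vs 2 or 6 vs 2 per 100 person-years gives (8 + 1.6)/(8 + 0.8) = 1.09 or (8 + 2.4)/(8 + 0.8) = 1.18. None of these rates is in the SAP, and the sum adds post-stop events without post-stop person-time.

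The reply does not remove the practical gap. In an ITT table, the percentage transfused by Week 52 omits recorded transfusions, and a comparative p-value is presented although Section 2.2 heads the exploratory endpoints as having no planned testing.

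**Conclusion.** The point holds in a limited form. The counting and censoring rules are certain from the text, as is the absence of any version using off-treatment transfusions. It follows that the Week 52 percentage depends on how early subjects stop. That the censoring is informative is possible, not established: it requires a raised transfusion risk after rescue, and a bias between arms requires unequal rescue as well.

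Neither size nor direction can be derived from the SAP. With a two-fold difference in rescue and a five- to ten-fold rise in risk for three months, all assumed, the rate ratio shifts by about 1 to 5%. With equal rescue there is no between-arm bias from rescue censoring. No co-primary or multiplicity-controlled result is affected, so this is a minor improvement.

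**What to change.** Keep the on-treatment analysis through end of treatment as planned and labelled. Add, for at least one transfusion by Week 52 and for time to first transfusion through Week 52, a version that counts all post-randomization transfusions regardless of treatment, measured from randomization and censored at study withdrawal, death or Week 52. Label the existing Week 52 tables as on-treatment.

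While editing Section 10.6.3.4, align the windows: events count to one day after the stop date, whereas censoring and person-time end on the stop date itself.

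The cost is some SAP wording and one further derivation from data already scheduled for collection. There are two limits. Some post-stop transfusions will occur under other anemia therapy and dilute the on-drug contrast. The added version cannot extend past Week 52, because the later schedule for discontinued subjects has no transfusion row; it therefore complements the longer on-treatment analysis and cannot replace it.
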